#### 9.1.4. Adverse Events of Special Interest

An adverse event of special interest (AESI) (serious or nonserious) is defined as an AE or SAE of scientific and medical concern specific to the Sponsor's product or program, for which ongoing monitoring and rapid communication by the Investigator to the Sponsor could be appropriate. The following events will be considered AESIs for this study and will be reported using the same process as for SAEs:

- New onset of inflammatory bowel disease (IBD) including ulcerative colitis or Crohn's disease
- Suicidal ideation

#### 9.2. Clinical Laboratory Evaluations

All summaries will be based on SI units. Blood and urine samples collected at the times indicated in the schedule of events (see Appendix 15.1) for clinical laboratory values (hematology, clinical chemistry, coagulation, urinalysis, and virology) will be analyzed by the central laboratory. COVID-19 testing will be performed on site or by the site's local laboratory. Clinical follicle stimulating hormone tests will be performed by the central laboratory. Additional blood, urine, and/or throat swab samples may be taken for safety tests.

Summary tables presenting observed values and changes from baseline will be presented for clinical laboratory tests with numeric values by treatment group for participants in the SAS. One table will be presented for each of hematology, and clinical chemistry parameter categories. Summary of observed values at screening for coagulation will be presented.

A table for categorical urinalysis values over time and screening virology will also be presented.

The number and proportion of participants with normal, high, and low values for each laboratory test (hematology and clinical chemistry) will be presented by visit and treatment group according to the reference ranges in the Central Lab Manual.

The number and proportion of participants with CTCAE Grades for each laboratory test (hematology and clinical chemistry) will be presented by visit and treatment group.

Shift tables summarizing the baseline and post-baseline timepoints results using normal range and CTCAE grading when available for clinical laboratory tests (hematology and clinical chemistry) will be displayed in cross-tabulations. Only during treatment endpoints are considered in this summary. Unscheduled assessments are included in the table for calculation of minimum post-baseline and maximum post-baseline values.

Corresponding box plots by visit and treatment of the observed values will also be presented for hematology parameters:

- Hemoglobin
- White blood cell count

- Neutrophils
- Lymphocytes
- Platelet count
- Erythrocyte sedimentation rate

and clinical chemistry parameters:

- Albumin
- Alkaline phosphatase
- Alanine aminotransferase
- Aspartate aminotransferase
- Total Bilirubin
- creatinine
- C-reactive protein
- Estimated glomerular filtration rate
- Gamma glutamyl transferase
- Lactate dehydrogenase
- Total cholesterol
- High-density lipoprotein cholesterol
- Low-density lipoprotein cholesterol
- Triglycerides

Different colors will be used for the treatment groups.

Laboratory test results for all visits including unscheduled assessments will be presented in a listing for the parameter with at least one abnormal value. The listing will be based of SAS.

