As IL-17 inhibition has the potential to result in infection, participants will be carefully monitored throughout the course of treatment. IL-17 inhibition has not been shown to increase the risk of TB infection or reactivation (Elewski 2021; Fowler 2020; Nogueira 2021). Thus, participants with positive IGRA testing are not required to be treated with prophylactic anti-TB therapy before or during the study if the participant is considered low risk for reactivation per Investigator judgment but will be carefully monitored for any sign of TB reactivation. A participant who develops active TB or pulmonary nontuberculous mycobacterial infection will be discontinued from study treatment. Absence of TB reactivation, despite not receiving anti-TB prophylaxis, will provide important information as to whether TB testing is required before treatment with DC-806.

Participants with newly diagnosed IBD (Crohn's disease or ulcerative colitis) during the study will be discontinued from study drug and referred, as appropriate, to a health care professional treating IBD, such as a gastroenterologist.

To evaluate the potential for suicidal ideation, a standard, validated questionnaire (the C-SSRS) will be administered to participants at Screening and at each subsequent study visit. Participants with active suicidal ideation as indicated by a positive response ("Yes") to either Question 4 or Question 5 of the "Since Last Visit" version of the C-SSRS will be discontinued from study treatment and referred immediately to a mental health professional and may be withdrawn from the study based upon the Investigator's judgment.

Although rare, potential for drug-induced hepatotoxicity is under constant surveillance by sponsors and regulators. A panel of standard clinical tests to evaluate liver function will be carefully monitored specifically to mitigate the risk of potential drug-induced liver injury. This study will ensure timely detection, evaluation, and follow-up of laboratory abnormalities in selected liver laboratory parameters to ensure the safety of participants.

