10.4.1 Management of Hepatotoxicity

For elevations in ALT or AST, the Investigator should assess the participant for potential druginduced liver injury and apply the standard of care for medical evaluation and treatment following any local guidelines. All abnormal laboratory tests considered clinically significant by the Investigator will be followed to a satisfactory resolution.

For elevations in ALT or AST >2×ULN in participants with normal levels at baseline and any elevation in ALT or AST >3×ULN, obtain repeat ALT, AST, ALP, and total bilirubin within 48 to 72 hours*. Specific toxicity management guidelines are as follows:

- Discontinue study drug if confirmed ALT or AST >3×ULN by repeat testing with new sample AND a total bilirubin >2×ULN (with no evidence of hemolysis and an ALP value <2×ULN or not available)
- Discontinue study drug if confirmed ALT or AST >3×ULN by repeat testing with new sample along with appearance of fatigue, nausea, vomiting, right upper quadrant pain, or tenderness, fever, rash, and/or eosinophilia (>5%)
- If confirmed ALT or AST >3×ULN but ≤5×ULN, total bilirubin ≤2×ULN and participant is asymptomatic, study drug may be continued after consultation with the Sponsor and CRO Medical Monitor
- If confirmed ALT or AST >5×ULN but ≤10×ULN, total bilirubin ≤2×ULN, hold study drug
 until ALT or AST ≤5×ULN⁺; study drug may be restarted only if a cause other than the study
 drug has been established and if liver test returns to baseline. Rechallenge must be in
 consultation with Sponsor and CRO Medical Monitor. If abnormalities worsen after drug is
 restarted, study drug must be discontinued.
- Discontinue study drug if confirmed ALT or AST >10×ULN

Obtain repeat ALT, AST, ALP, and total bilirubin approximately every 3 days following receipt of previous laboratory results until ALT and AST are at or below approximate baseline levels for the participant. The frequency of retesting may be decreased to once a week or less if abnormalities are stabilized and participant is asymptomatic. If ALT and/or AST abnormalities worsen or remain >5×ULN for ≥14 consecutive days, study drug should be discontinued.

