#### 4. General Statistical Considerations

Data collected in this study will be presented using summary tables, participant data listings and figures. For ordinal-scaled variables, a combination of presentations may be employed as appropriate: frequency and percentage of observations within a category and means and standard deviations of the scores of the categories. For categorical and ordinal variables, percentages will be calculated based on the N of the analysis set and number of participants with missing data will also be included. All by-visit summaries will use assessments done at the scheduled visits. If multiple assessments or measurements are done at a single scheduled visit, only the latest such assessment/measurement will be included in the summary. All data will be included in the listings.

Continuous variables will be summarized using the number of participants, mean, standard deviation (SD), median, minimum, and maximum values. The minimum and maximum values will be presented to the same level of precision as the data. The mean and median will be presented to one decimal place greater than the level of precision in the data, and the SD will be presented to two decimal places greater than the level of precision in the data. Categorical summaries will include the frequency counts of each category, and the percentage displayed to one decimal place. In the case of a zero count, the percentage will be suppressed to draw attention to the non-zero counts.

Unless otherwise specified, all confidence intervals (CI) will be 2-sided and performed using a 5% significance level. P-values will be displayed in the following format: 0.9999. Any p-value less than 0.0001 will be displayed as <0.0001. Any p-value greater than 0.9999 will be displayed as >0.9999.

The reference date for the calculation of study days will be the date of the first dose at Day 1. For events/assessments on or after the treatment start date, the study day of events/assessments from treatment start date is calculated as the date of event minus the reference date + 1. For events/assessments before the treatment start date, the study day of events/assessments is defined as the date of assessment minus the reference date.

Baseline will be defined as the last non-missing assessment value before the first dose of study drug.

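### SAP 9.2 has no by-arm count of the protocol's combined liver criterion, and a liver peak seen only at an unscheduled retest after drug stop reaches only a listing

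*SAP*

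**What the plan says.** Protocol 2.4 gives the purpose of liver testing: "A panel of standard clinical tests to evaluate liver function will be carefully monitored specifically to mitigate the risk of potential drug-induced liver injury". Protocol 10.4.1 sets a joint criterion: "Discontinue study drug if confirmed ALT or AST >3×ULN by repeat testing with new sample AND a total bilirubin >2×ULN". It is qualified by absence of hemolysis and by ALP below 2×ULN or unavailable. The section also sets bands for confirmed ALT or AST at 3×, 5× and 10×ULN. After a qualifying elevation the site must "obtain repeat ALT, AST, ALP, and total bilirubin within 48 to 72 hours". Serial testing then continues until ALT and AST are near the participant's baseline: "Obtain repeat ALT, AST, ALP, and total bilirubin approximately every 3 days following receipt of previous laboratory results". Less frequent testing is allowed once values are stable.

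SAP 9.2 tabulates each analyte alone. It plans observed values and changes, normal/high/low counts, grades ("The number and proportion of participants with CTCAE Grades for each laboratory test (hematology and clinical chemistry) will be presented by visit"), shift tables and box plots. Two data rules apply:

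- SAP 4: "All by-visit summaries will use assessments done at the scheduled visits". If a visit has several values, the latest is used, not the worst.
- SAP 9.2, on the shift tables: "Only during treatment endpoints are considered in this summary". Inside that window, unscheduled values count toward the post-baseline minimum and maximum.

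A listing carries all results, unscheduled ones included, for any parameter with an abnormal value.

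**The concern.** There are two gaps. First, the protocol's criterion concerns two abnormalities in the same participant, and tables built one analyte at a time cannot show that. None of the planned laboratory tables uses the protocol's ×ULN cut-points either.

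Second, participants taken off drug because of liver tests are the ones the protocol retests most often. The two data rules together keep their unscheduled post-stop values out of every laboratory summary. Someone whose ALT or bilirubin goes on rising after the stop, and has fallen again by the next scheduled visit, would be shown at a lower level than was measured.

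Comparing safety with placebo is one of the two primary objectives (Protocol 3.0), in a study meant to guide dose. The stake is a by-arm liver summary that may be understated and that omits the one combination the protocol singles out.

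**Working it through.** The documents give no power, rate or margin for liver injury, so there is no planned figure to reproduce beyond the arm sizes: 5 × 45 = 225 in total and 4 × 45 = 180 on DC-806 (SAP 4.2).

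**1. Where each liver value goes.** This applies SAP 4 and 9.2 to the visits in Protocol 1.3 and 7.1.

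| Liver value | By-visit tables | Worst-value shift table | Listing |
|---|---|---|---|
| Scheduled, on drug | yes | yes | yes |
| Unscheduled retest, on drug | no | yes | yes |
| Unscheduled retest during a hold | no | unclear, window undefined | yes |
| Scheduled visit after drug stop, Early Termination or Day 115 | yes | no, if the window closes at drug stop | yes |
| Unscheduled retest after drug stop | no | no, if the window closes at drug stop | yes |

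Only the last row is missing from both kinds of table. The window is also unclear for completers: the last dose is on Day 84 and the final treatment-period visit is Day 85 (Protocol 6.3), so a strict reading could leave Day 85 out of the shift table.

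**2. How many values the last row can hold.** Chemistry is scheduled on Days 1, 8, 15, 29, 57, 85 and 115. With one retest every 3 days, the number falling strictly between two visits is floor((gap − 1)/3):

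- Days 1 to 8 and 8 to 15: gap 7, floor(6/3) = 2
- Days 15 to 29: gap 14, floor(13/3) = 4
- Days 29 to 57 and 57 to 85: gap 28, floor(27/3) = 9
- Days 85 to 115: gap 30, floor(29/3) = 9

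These are upper figures, because the protocol counts the 3 days from receipt of the previous result and allows weekly or rarer testing once values are stable.

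**3. Whether single-analyte counts give the joint count.** With k participants above the ALT/AST cut and m above the bilirubin cut in an arm of 45, the joint count lies between max(0, k + m − 45) and min(k, m). For k = m = 2 the range is 0 to 2; for k = m = 3 it is 0 to 3. The counts are illustrative. The joint number is not identified.

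**4. What a joint count could support.** With zero cases, the exact two-sided 95% upper limit is 1 − 0.025^(1/n): 2.0% for n = 180 and 7.9% for n = 45. The chance of at least one case is 1 − (1 − p)^n. For assumed true rates of 0.5%, 1% and 2% (not from the documents), it is 20%, 36% and 60% in one arm of 45, and 59%, 84% and 97% in the 180 on DC-806. Any cases would be few, so leaving one out would matter.

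**The case against.** A reader might infer that a liver signal would appear in no table by arm. The documents do not support that. High/low, CTCAE-grade and shift tables are all by treatment group. Clinically significant laboratory abnormalities are to be reported as adverse events (Protocol 8.2.5.5). TEAEs run to the Follow-up Visit and are tabulated by term, severity, relationship, seriousness and discontinuation (SAP 9.1, 9.1.1). Reasons for stopping treatment are summarised (SAP 5.1).

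A reader might also infer that the mandated retests are discarded in general. They are not. On-drug retests enter the shift-table maximum. Participants stopped for an adverse event or laboratory abnormality keep attending scheduled visits until it settles (Protocol 7.1), and those values enter by-visit tables. Because the joint criterion is itself a discontinuation trigger and requires a confirmed ALT or AST, a typical case would be found before discontinuation.

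It can further be said that neither document makes hepatic events an AESI, that Protocol 9.3 calls the analysis descriptive and exploratory, that a handful of cases can be matched from the listing, and that the IDMC shells, which are not available here, may hold a joint table (SAP 1).

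All of this limits the consequence, but it does not supply the missing count. Adverse event capture depends on the investigator's judgement of significance, and a listing is not a count by arm. IDMC outputs, whatever they contain, are not the SAP's planned outputs.

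**Conclusion.** The point holds as a modest reporting gap. The readable SAP has no by-arm count of the combined criterion or of the protocol's ×ULN bands. A peak seen only at an unscheduled retest after drug stop is in no laboratory summary table. Combined cases would have to be rebuilt from listings or would depend on adverse event reporting.

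The second part assumes that the treatment window closes when drug stops, which the SAP does not state. How often a participant would first cross the joint threshold after stopping, and between scheduled visits, cannot be estimated from the documents. The 2.0% and 7.9% limits follow from sample size alone and do not measure the gap. The documents do not give CTCAE laboratory cut-points, so these were not compared with the ×ULN bands.

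The change is worth making because it is cheap, serves a primary safety objective and fits the SAP's own pattern. SAP 9.3 and 9.5 already plan threshold tables for vital signs and ECG, and the ECG table includes QTcF above 500, the same value as the discontinuation threshold in Protocol 7.1.

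**What to change.** In SAP 9.2, add one table by treatment group for the Safety Analysis Set. It counts participants with post-baseline ALT or AST above 3×, 5× and 10×ULN, with total bilirubin above 2×ULN, and with the combined criterion of Protocol 10.4.1.

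- Pair ALT/AST with bilirubin within a prespecified time window, so that unrelated peaks are not counted as joint.
- Flag confirmation on a new sample, ALP below 2×ULN or unavailable, hemolysis, and known Gilbert syndrome (Protocol 5.2 admits such participants with isolated raised indirect bilirubin).
- For this table, and for the liver parameters in the worst-value shift table, use all scheduled and unscheduled values from first dose through the Follow-up Visit, which is the TEAE window of SAP 9.1. Add an on-drug/off-drug flag.
- Define the treatment window for the other laboratory tables, including whether Day 85 and periods on hold belong to it.
- Optionally, add a scatter plot of peak ALT against peak bilirubin, both in ×ULN.

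The cost is SAP wording and a little programming on data already collected. The downside is that off-drug values enter the liver worst-value summary, which the flag makes visible. No clinical management rule is altered.

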#### 9.3. Vital Sign Measurements

Body temperature (ear or oral), respiratory rate, seated blood pressure, and heart rate will be assessed at the times indicated in the schedule of events (see Appendix 15.1). Blood pressure and heart rate will be measured after the participant has been resting quietly for  $\geq$ 5 minutes. Summary tables presenting observed values and changes from baseline will be presented for vital sign data, including systolic blood pressure (mmHg), diastolic blood pressure (mmHg), temperature (°C), heart rate (beats/min), and respiratory rate (breaths/minute), by treatment group for participants in the SAS. Changes from baseline to each scheduled post-baseline visit will be presented.

Substantial changes from baseline in clinically significant vital signs results will be presented by treatment group based on the following criteria:

- For Systolic Blood Pressure: High is defined as ≥160 mmHg and increase from baseline>40 mmHg; and Low is defined as <90 mmHg and decrease from baseline >20 mmHg.
- For Diastolic Blood Pressure: High is defined as ≥100 mmHg and increase from baseline>20 mmHg; and Low is defined as <60 mmHg and decrease from baseline >10 mmHg; or and Low\* is defined as <60 mmHg and decrease from baseline >20 mmHg.
- For Heart Rate: High is defined as >100 beats/min and increase from baseline>20 beats/min; and Low is defined as <60 beats/min and decrease from baseline >20 beats/min.
- For Respiratory Rate: High is defined as >24 beats/min; and Low is defined as <10 beats/min when baseline is between 10 and 24 beats/min.

• For Temperature, High is defined as ≥38 °C; and Low is defined as <35 °C when baseline is between 35 and 38 (excluded) °C.

Scheduled and unscheduled on-treatment assessments are used in the substantial changes from baseline summary outputs.

Vital Sign results for all visits including unscheduled will be presented in a listing for the parameter with at least one abnormal value. The listing will be displayed for the SAS.

#### 9.4. Physical Examination

A full physical examination will be assessed (see Appendix 15.1) on the general appearance; ears, nose, and throat; head, neck, and thyroid; cardiovascular; dermatological, respiratory; lymph nodes; abdomen; musculoskeletal and nervous system. A targeted physical examination will involve assessment of the following: cardiovascular; dermatological, respiratory; abdomen and, any other system if deemed necessary. The number and proportion of participants with abnormal and normal results and those with assessments not done will be presented for the SAS by assessment, visit and treatment group.

A listing will also be displayed for the SAS.

#### 9.5. Electrocardiogram

Triplicate 12-lead Electrocardiogram (ECG) will be done at the visits specified in the schedule of events (see Appendix 15.1). Summary tables will be presented for PR Interval (msec), QRS Duration (msec), QT Interval (msec), and QTcF interval (msec) by treatment group for participants in the SAS. For triplicate ECGs, the average of the triplicate values will be used to determine the value at that time point. The shift of the overall ECG interpretation from baseline over time will be summarized for the SAS. For triplicate ECGs, the best interpretation of the triplicate values at pre-dose on Day 1 will be used; the worst interpretation of the triplicate values will be used at each post-baseline time point.

Substantial changes from baseline in clinically significant electrocardiogram results will be presented by treatment group based on the following criteria:

- QT Interval: New > 450 / New > 480 / New > 500 / Increase from baseline > 30 / Increase from baseline > 60
- QTcF Interval: New > 450 / New > 480 / New > 500 / Increase from baseline > 30 / Increase from baseline > 60
- QRS Duration: Increase > 25% and to a value > 110
- PR Interval: Increase > 25% and to a value > 200

Note: the average value will be used for substantial changes if triplicate ECGs were performed. Scheduled and unscheduled on-treatment assessments are used in the substantial changes summary outputs.

A corresponding listing on abnormal ECG results for the SAS will also be presented.

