8.2.4 Electrocardiograms

12-lead ECGs will be measured after the participant has been in the supine position for a minimum of 5 minutes. Single 12-lead safety ECGs (Screening, Day 85/Early Termination, and Day 115 will be read by the Investigator to identify any clinically significant abnormalities that would exclude the participant from further study participation. Triplicate ECGs will be obtained approximately 1 minute apart at predose and at 1 hour after dosing on Days 1, 15, and 57. Blood draws should be avoided in the period immediately before ECG measurement and activity should be controlled as much as possible to minimize variability due to effects of physiologic stress.

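### The ECG interpretation shift table takes the best of three readings at baseline and the worst of three afterwards, so it shows worsening in every arm without any drug effect

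*SAP*

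**What the plan says.** SAP 9.5 plans this output: "The shift of the overall ECG interpretation from baseline over time will be summarized for the SAS". For its baseline axis, "the best interpretation of the triplicate values at pre-dose on Day 1 will be used"; for its other axis, "the worst interpretation of the triplicate values will be used at each post-baseline time point". No reason for the difference is given, and the interpretation categories are not defined there.

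The same section treats the numerical ECG parameters alike before and after dosing: "For triplicate ECGs, the average of the triplicate values will be used to determine the value at that time point". For the QT, QTcF, QRS and PR threshold summaries, "the average value will be used for substantial changes if triplicate ECGs were performed". It also plans a listing: "A corresponding listing on abnormal ECG results for the SAS will also be presented".

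Protocol 8.2.4 sets the triplicates "approximately 1 minute apart at predose and at 1 hour after dosing on Days 1, 15, and 57". That makes one baseline triplicate (Day 1 predose) and five later ones (Day 1 at 1 hour, and two each on Days 15 and 57). The remaining recordings are not triplicate: "Single 12-lead safety ECGs (Screening, Day 85/Early Termination, and Day 115". SAP 9.5 does not say how a single reading at Day 85/Early Termination or Day 115 is to be set against a best-of-three baseline.

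**The concern.** A shift table is read as change from baseline. If baseline is the most favourable of three readings and every later triplicate is the least favourable, a participant whose readings merely vary is entered as having worsened. A participant can be entered as improved only if all three baseline readings were abnormal and all three later ones normal.

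Two readings of the table are then unsafe. Within an arm, the count of normal-to-abnormal shifts cannot be taken as change on treatment. Over time, a fall at Day 85 or Day 115 may be only the move from three readings to one, yet it could be read as abnormalities resolving when treatment ends. Protocol 2.4 mentions ECG findings at high doses in nonclinical work and says ECGs will be monitored, so this display will be looked at. It is the only by-arm summary of the overall interpretation in that section.

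**Working it through.** The plan states no figure for this table, so there is none to reproduce. Assumed, because the documents do not give them: two categories (normal, abnormal), a per-reading abnormal rate p, and no drug effect.

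**Independent readings.**
- SAP rule, worsening: (1 − p³) × (1 − (1 − p)³)
- SAP rule, improvement: p³ × (1 − p)³
- Single reading at both times, worsening: p(1 − p)
- Middle of three at both times, worsening: m(1 − m), where m = 3p²(1 − p) + p³
- Best-of-three baseline against one later reading (Days 85 and 115), worsening: (1 − p³) × p

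At p = 5%: 0.999875 × 0.142625 = 14.3% worsening and 0.000125 × 0.857375 = 0.01% improvement. Single/single gives 0.05 × 0.95 = 4.8%. With m = 0.00725, middle/middle gives 0.7% in each direction. At Days 85 and 115 the result is 0.999875 × 0.05 = 5.0%.

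Across p, worsening under the SAP rule against single/single is 5.9% against 2.0% (p = 2%), 14.3% against 4.8% (5%), 27.1% against 9.0% (10%) and 48.4% against 16.0% (20%).

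**Correlated readings.** Tracings about a minute apart will agree more than independence allows. Take a latent score √a·person + √v·visit + √(1 − a − v)·reading, all standard normal, abnormal above the point exceeded with probability p. The person term is shared across visits and the visit term within a triplicate. At p = 5% (correlated rows are good to about 0.1 point):

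| Shares a / v | SAP rule: worsening | SAP rule: improvement | Days 85/115: worsening | Middle/middle: each direction |
|---|---|---|---|---|
| 0 / 0 | 14.3% | 0.01% | 5.0% | 0.7% |
| 0.5 / 0.2 | 9.5% | 0.4% | 4.5% | 2.6% |
| 0.7 / 0.2 | 6.2% | 0.9% | 3.7% | 2.6% |
| 0.6 / 0.39 | 4.3% | 2.6% | 3.6% | 3.4% |

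In an arm of 45, worsening at each triplicate time point is 45 × 0.143 = 6.4 participants if independent, 45 × 0.095 = 4.3 in the second row and 45 × 0.043 = 1.9 in the last. Any rule used at both times balances: worst/worst in the second row gives 6.4% against 6.5%.

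**Comparison with placebo.** The SAP plans no test of this table; Fisher's exact test at 45 per arm, two-sided 5%, serves only as a measure of contrast.
- *The drug makes all three readings abnormal in an extra share d of participants, with independent noise.* The shift rate on drug is P(baseline normal) × (w + d(1 − w)), where w is the chance of a noise-only abnormal result after baseline. At p = 5%, d = 20%: 14.3% against 31.4% under the SAP rule (power 39%), and 0.7% against 20.4% under middle/middle (86%). At p = 10%, d = 20%, power is 24% against 75%. At d = 10%, it is about 8% to 12% against 22% to 27% for p of 10% and 5%.
- *The drug raises the per-reading rate.* At p = 10%, shares 0.5/0.2, rate tripled: 16.8% against 44.6% under the SAP rule (power 77%), and 5.1% against 22.4% under middle/middle (59%). Over 24 such scenarios the SAP rule had at least the power of middle/middle in 23; the exception was 99.8% against 99.9%.

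Worst/worst had lower power than best/worst in every scenario run. Where dilution occurs, it therefore comes from taking the worst of three after baseline, not from the asymmetry.

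**The case against.** The strongest case is that this is a deliberate, conservative safety convention in one descriptive table. Protocol 9.3 calls the analysis descriptive and exploratory, and placebo is shown alongside under the same rule. Interval summaries and threshold outputs use triplicate means throughout, abnormal ECGs are listed, clinically significant ECG abnormalities are adverse events (Protocol 10.3.1.1), and a confirmed long QTcF has its own rule in Protocol 7.1. A category cannot be averaged, so a rule different from that for the intervals is not in itself an error. A 2-of-3 rule would drop a lone abnormal tracing, possibly a real intermittent one, and with more than two categories there may be no majority. The 14% also assumes independence between tracings a minute apart, which is the extreme case.

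Most of this stands, and it limits the point. A reader might infer that the rule hides a real drug effect. The documents do not support that: the rule is identical in all arms, so it adds background rather than between-arm bias, and whether the contrast weakens depends on how the drug acts, on which the documents are silent. Power figures should not be quoted as the reason for change.

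What the objection does not answer is the within-arm imbalance, which persists even with nearly identical readings, or the unlabelled switch from triplicate to single ECGs. Conservatism explains taking the worst reading after baseline; it does not make the resulting counts a measure of change.

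**Conclusion.** The point holds, confined to the overall-interpretation shift table. The SAP rule inflates normal-to-abnormal shifts and suppresses the reverse in every arm. At an assumed 5% per-reading rate, the imbalance runs from about 14% against 0% (independent readings) down to 4.3% against 2.6% (nearly identical readings). Moderate correlation lies between, at 6% to 10% against 0.4% to 0.9%. The apparent fall at Days 85 and 115 is an artefact of the same rule, about 14% to 5% or 10% to 4.5%, and shrinks as readings agree more closely. All sizes rest on assumed rates and correlations and on two categories.

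There is no bias between arms. Contrast with placebo can be diluted if an effect is sustained across all three tracings; it is generally not diluted if the drug raises the per-reading rate. This is a cheap improvement to one safety display and does not cast doubt on the ECG evaluation as a whole.

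**What to change.** In SAP 9.5, make the main shift table use one rule at baseline and after: the middle of the three ordered interpretations. With two categories this equals 2-of-3, and with more it is still defined provided the categories are ordered, so list them in order. Keep the best/worst version as a supplementary conservative display, described as such, so that a lone abnormal tracing stays visible there as well as in the listing.

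Label Day 85/Early Termination and Day 115 as single readings, and state that their counts are not comparable with triplicate visits. The label is needed under the new rule too. With independent readings at p = 5%, a middle-of-three baseline against one later reading gives (1 − 0.00725) × 0.05 = 5.0% worsening, compared with 0.7% at triplicate visits, so the artefact would change direction rather than disappear.

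The cost is a few SAP sentences and one extra descriptive table, with no new data.
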